- 2. Safety follow-up: Safety follow-up visit should be conducted at 30, 60, 90 days (\pm 3 days) after the last dose of investigational product. If the EOT visit occurs in the time window of the first safety follow-up visit ($30\pm$ 3 days), the same tests and examinations don't need to be repeated. It is recommended to complete all protocol required follow-up evaluations for the safety follow-up at 60 ± 3 days and $90\pm$ 3 days after the last dose, or AEs and concomitant medications can be collected through phone call. Safety follow-up period refers to the 90 days after the last dose of the investigational treatment or the start of new anti-cancer treatment, whichever occurs earlier.
- 3. Radiology follow-up: Apart from subjects who discontinue treatment due to radiological disease progression, tumor assessment should be performed at prespecified regular time points until radiological disease progression, the start of new anti-cancer treatment, death, or the end of this trial, whichever occurs first.
- 4. Survival follow-up: Survival status will be assessed every 12 weeks by telephone after the last dose of investigational product.
- 5. Concomitant medications: All concomitant medications received from 30 days before the screening will be recorded until 90 days after the last dose of study treatment or the start of new anti-cancer treatment, whichever occurs first.
- 6. Adverse events (AEs): All AEs will be recorded from signing informed consent to 90 days after the last dose of investigational product or starting new anticancer therapy, whichever comes first. Thereafter only study treatment-related SAEs need to be recorded. AEs that occur after the safety follow-up visit can be recorded by telephone follow-up 60 days and 90 days after the last dose.
- 7. Electrocardiogram (ECG): ECG will be performed at screening, EOT visit, and safety follow-up visit. The frequency of ECGs may be increased if clinically indicated.
- 8. Height, weight, and vital signs: Height will only be measured at screening, weight at screening, EOT visit, and safety follow-up visit. Vital signs include temperature, pulse, respiratory rate, and blood pressure.
- 9. Physical examination and ECOG performance status: Overall physical examination will be performed at screening, EOT visit, and safety follow-up visit. The lymphoma-specific physical examination will be performed during the treatment period.

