- Deaths with an unknown cause should always be reported as an SAE. Every effort should be made to identify the cause of death. An autopsy may be helpful in the assessment of the cause of death, and if performed a copy of the autopsy results should be forwarded to the representative of the sponsor in an expedited way within the predetermined timeframe.

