7.2.2 Serious Adverse Event Reporting

Any SAE occurring from the time of ICF signing to 90 days after the last dose of investigational product or the start of new anti-cancer therapy, whichever occurs earlier, must be reported to the designated representative of CRO or the sponsor **no later than 24 hours** when it gets learned of, regardless of causality with the investigational product. After the safety follow-up period, only treatment-related SAEs need to be recorded and reported.

Once an SAE occurs, the investigator should:

• Immediately take appropriate treatment measures for the subject and report to the sponsor as described above, and to drug regulatory authorities, health administrative authorities, and the Ethics Committee according to the local requirements.

Complete the SAE module in the EDC system, after which an automated email will be sent to the designated sponsor representative. In case EDC is down, all applicable modules of the sponsor's SAE form will be completed by the investigator/site staff. The investigator must assess the relationship of each SAE to each specific component of study treatment, complete and sign the SAE Report Form, and submit the completed form within 24 hours to the sponsor pharmacovigilance representative. Follow-up information is submitted in a new SAE report form and marked as the follow-up information of a previously reported SAE.

Any SAE that is unresolved at the end of study or subject withdrawal must be followed up until any of the following condition occurs:

- Event resolves; or
- Event stabilizes; or
- Event returns to baseline level (if baseline level available); or
- The event can be attributable to factors related with a medication other than the investigational product or unrelated with the investigator's behavior, or further information is unable to be obtained (when the subject or medical staff refuses to provide more information or when there's evidence showing the subject is lost to follow-up despite every effort made).

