7.3.1 Causality Assessment

The investigator should determine the relationship between the AE and the investigational product based on the following criteria:

- **Definitely related:** there is a rational temporal relationship of the occurrence of an AE including clinical laboratory finding to the administration of the investigational product. The investigational product can explain the AE more than any other reason (for example the underlying disease, environmental or toxic factors, or other treatment received by the subject); the reaction after discontinuation of investigational treatment is clinically reasonable.
- **Possibly related:** there is a rational temporal relationship of the occurrence of an AE including clinical laboratory finding to the administration of the investigational product. The investigational product can explain the AE with equal rationality with any other reason (for example the underlying disease, environmental or toxic factors, or other treatment received by the subject); information on post-discontinuation reaction is unavailable or unclear.
- Unlikely related: other reasons (for example the underlying disease, environmental or toxic factors, or other treatment received by the subject) explain the AE (including laboratory findings) more than the investigational product
- **Definitely unrelated:** there is no rational temporal relationship of the occurrence of an AE to the administration of the investigational product. The AE has other more remarkable reasons (for example the underlying disease, environmental or toxic factors, or other treatment received by the subject).
- Not determined: the above information is not available and with no complementary data, making causality not determined.

Definitely related, possibly related, and not determined events are counted as related adverse events when statistical analyses for adverse events are performed.

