8.4 SAFETY ANALYSES

The safety analysis will be performed for the SAS population.

Descriptive statistics will be performed to summarize the exposure of the investigational product, which may contain number of cycles, administrations and dose levels, etc.

All adverse events will be described according to MedDRA and graded according to the NCI CTCAE v4.03. All adverse events that occurred during or after investigational product administration will be summarized by NCI CTCAE grade. In addition, serious adverse events, severe adverse events (Grade 3, 4, or 5 events), drug-related AEs, and AEs causing discontinuation or dose modification of the investigational product will each be summarized. Multiple occurrences of the same event will be only counted once for the most severe event. The proportion of subjects with more than one adverse event will be reported.

All deaths that occur during the study or within the defined follow-up period after the last dose/discontinuation of investigational product will be reported.

Specific laboratory tests, vital signs, physical examinations, and 12-lead ECGs and their changes compared with baseline will be summarized. The values at baseline and each time point post-baseline will be presented by crosstabs, when appropriate.

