Descriptive statistics will be performed to summarize the exposure to study drug, including duration of treatment exposure in months, number of cycles, cumulative actual dose. etc.

Adverse Events

All AEs will be coded using the MedDRA dictionary. The severity will be graded using the National Cancer Institute (NCI) Common Terminology Criteria for Adverse Events (CTCAE), version 4.03.

The number of subjects experiencing treatment-emergent adverse events (TEAEs) will be summarized. TEAE was defined as:

- AE occurred on or after study treatment initiation or
- AE occurred before study treatment initiation but worsened on or after study treatment initiation

In addition, serious TEAEs, severe TEAEs (Grade ≥ 3), treatment-related TEAEs, immune-related TEAEs (assessed by the investigator), infusion-related reactions, and TEAEs leading to study drug discontinuation or interruption will also be summarized.

A subject experiencing multiple AEs under the same PT or SOC will be counted only once for that PT or SOC by maximum severity.

Adverse events of special interest (AESIs) will be assessed by the sponsor. The following summaries will be provided:

- For each AESI category, the number and percentage of subjects who experienced at least one of the following events will be summarized by treatment group: AESI, serious AESI, AESI with NCI-CTCAE grades 3-5, immune-related adverse events evaluated by investigator, AESIs resulting in CS1001/placebo discontinuation, AESIs resulting in CS1001/placebo interruption (including AESIs resulting in delayed treatment cycle of CS1001/placebo), AESIs resulting in death, AESIs requiring systemic corticosteroid, and AESIs requiring high-dose systemic corticosteroid.
- AESIs by the most serious NCI-CTCAE grade, PT and treatment group will be summarized.
- AESIs by PT, outcome of adverse events and treatment group will be summarized.
- Time to onset and duration of each AESI will be summarized using Kaplan-Meier method.
- The number and percentage of subjects who experienced thyroid or diabetes mellitus related AESI at least once and used corresponding concomitant medications will be summarized.

All AEs will be listed by subject.

Death

Death reasons will be summarized. All deaths will be listed by subject.

Laboratory Data

The laboratory data will be converted to Standard International (SI) units. The absolute value and change from baseline of each lab parameters will be summarized by scheduled visit.

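### The SAP's treatment-emergent definition has no end date, so the all-TEAE, serious and Grade 3 or higher tables mix full AE collection with a later period selected mainly by relatedness

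*SAP*

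**What the plan says.** **Analysis rule.** SAP 4.7.2 counts an event as treatment-emergent under either of two limbs: "AE occurred on or after study treatment initiation or" "AE occurred before study treatment initiation but worsened on or after study treatment initiation". The serious, Grade 3 or higher and treatment-related TEAE summaries all rest on this definition, with each subject counted once per term at maximum severity. Protocol 8.4 gives no end date either: "All adverse events that occurred during or after investigational product administration will be summarized by NCI CTCAE grade".

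**Collection rule.** Note 6 to the protocol's Schedule of Activities (Table 1) has all AEs recorded from consent to "90 days after the last dose of investigational product or starting new anticancer therapy, whichever comes first". It continues: "Thereafter only study treatment-related SAEs need to be recorded". Section 7.2.2 repeats this for serious events: "After the safety follow-up period, only treatment-related SAEs need to be recorded and reported". For the survival follow-up period, Table 7 (Section 7.1.3) has No for new AEs and for non-drug-related SAEs, and Yes for ongoing AEs and for drug-related SAEs.

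**Deaths.** The Deaths part of Section 7.1.3 covers deaths during the study or within protocol-defined follow-up. A death clearly due to progression is not an SAE. For a death not clearly due to progression, the AE that caused it is an SAE. For the rest: "Deaths with an unknown cause should always be reported as an SAE". Earlier in the same section, all deaths after progression and during survival follow-up go into the eCRF, with no statement that they are SAEs.

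**Relatedness.** Section 7.3.1 lists five causality categories and states the counting rule: "Definitely related, possibly related, and not determined events are counted as related adverse events". The SAP does not repeat that rule.

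**The concern.** A TEAE percentage is readable only if every event that could count had the same chance of being recorded. Here the analysis window is open-ended and the collection window is not. Consider two SAEs of the same kind, both judged unrelated: one just before the cut-off is in the serious TEAE table, and one just after it is not. If the second is judged related, it is in. Past the cut-off, the investigator's causality call largely decides whether an event exists in the data at all.

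The cut-off can also be the start of new anti-cancer therapy, so the later period includes time on other treatment. The trial has one arm, so no comparator shares the distortion. The SAP's analysis-timing section also plans to repeat all analyses for a US filing once every responder has at least 6 months of follow-up from first response. For subjects already past their cut-off, that later data cut can add new events only under the selective rule.

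**Working it through.** The documents state no figure on this point, so there is nothing to reproduce. The check is a comparison of rules, followed by an illustration of scale.

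**Step 1. Collection against counting.**

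| Type of event | Collected inside the window | Collected after it | Would be a TEAE if collected after it |
|---|---|---|---|
| New non-serious AE | Yes | No | Yes |
| New SAE, not drug-related | Yes | No | Yes |
| New SAE, drug-related | Yes | Yes | Yes |
| Ongoing AE | Yes | Yes, still followed | Already a TEAE; later worsening can raise its maximum grade |
| Death of unknown cause, or not clearly due to progression | Yes, as an SAE | Unclear (Step 3) | Yes, if entered as an SAE |

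The window closes at the earlier of 90 days after the last dose or new anti-cancer therapy. The last column says Yes throughout because neither limb of the definition has an upper limit.

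**Step 2. What the serious TEAE percentage estimates.** Leave late deaths aside. Let N be the subjects treated, A those with any SAE inside the window, B those whose first SAE is late and drug-related (collected), and C those whose only SAE is late and not drug-related (not collected).

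- Reported: (A + B)/N
- Rate inside the window: A/N
- Rate over all follow-up: (A + B + C)/N

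The reported rate equals the second only if B = 0 and the third only if C = 0. The Grade 3 or higher and all-TEAE tables have the same structure, and they also lack late non-serious events. For drug-related SAEs the reported rate is (related inside the window + first related after it)/N. No term is missing, so that count is not distorted by the mix.

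**Step 3. Late deaths of unknown cause.** Section 7.1.3 says such deaths are always SAEs, over a scope that is not limited to 90 days. Table 7 and Section 7.2.2 limit late SAE recording to drug-related events. These rules conflict, and the SAP does not say which governs. If the death enters, it is serious and Grade 5. It is counted as related only if the investigator rates it definitely related, possibly related or not determined. Nothing in the documents requires an unknown-cause death to be rated 'not determined'. The labels also differ: the category is 'not evaluable' in 7.1.3 and 'not determined' in 7.3.1.

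**Step 4. Scale, for illustration only.** Assume 80 treated subjects (the planned enrolment is approximately 80), no other related death, and k late deaths that both enter as SAEs and are rated 'not determined'. The documents do not give k; 0 to 4 is an assumed range. The rate is k/80, so each death adds 1/80 = 1.25 percentage points. The exact 95% limits are the 0.025 quantile of Beta(k, 81 − k), taken as 0 when k = 0, and the 0.975 quantile of Beta(k + 1, 80 − k).

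| k | Rate | Exact 95% CI |
|---|---|---|
| 0 | 0% | 0 to 4.5% |
| 1 | 1.25% | 0.03 to 6.8% |
| 2 | 2.5% | 0.3 to 8.7% |
| 3 | 3.75% | 0.8 to 10.6% |
| 4 | 5.0% | 1.4 to 12.3% |

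**The case against.** The strongest reply has four parts.

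- **An open window is conservative for safety.** Any late drug-related SAE stays in the main tables, and immune-related events can appear late. This stands as a reason to keep those events prominent. It does not rescue the percentage, because the open window captures only the late events that the collection rule lets through.
- **Late deaths are already visible.** The SAP summarises reasons for death and lists all deaths and all AEs by subject. True, but it specifies no split by time since last dose or by new therapy.
- **Late deaths need not become related events.** A reader might infer that every late death of unknown cause is automatically tabulated as a related Grade 5 TEAE. The documents do not support that. Entry as an SAE is unsettled, and an investigator who knows of progression, later treatment and a long gap since the last dose could choose 'unlikely related' or 'definitely unrelated', neither of which is counted. Nor does the SAP name a separate table of related fatal TEAEs.
- **The number of such deaths is unknown.** The protocol's background cites a median OS below 6.4 months on salvage chemotherapy. That says nothing about how many deaths lack a known cause, and deaths clearly due to progression are not SAEs. The objection stands, so Step 4 shows scale and is not an estimate.

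**Conclusion.** The point holds in a limited form. The TEAE definition has a start and no end, full AE collection has an end, and the all-TEAE, serious and Grade 3 or higher tables therefore pool two collection rules. The selective collection comes from the protocol; the SAP's part is that it does not cut the analysis off where full collection stops.

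Two further inferences are tempting and should not be drawn. The first is that only drug-related SAEs and unknown-cause deaths can enter late. If the death rules reach past the window, the AE behind any death not clearly due to progression enters too, and ongoing AEs are still followed throughout. The second is that the drug-related SAE count is itself inflated by the mix. It is not, because one rule applies to those events in all phases.

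The size cannot be computed from the documents. The 1.25 percentage points per death rests on 80 treated subjects and on the death both entering as an SAE and being rated 'not determined'. This is an inexpensive improvement that should be made before the tables are produced; it does not touch the primary endpoint.

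**What to change.** 1. In SAP 4.7.2, end the TEAE period at the earlier of 90 days after the last dose or the start of new anti-cancer therapy, for both limbs. State whether worsening after that date, in an AE that began inside the window, counts toward maximum severity.
2. Report later drug-related SAEs, and later deaths reported as SAEs, in a separate table and listing placed next to the main one, with days since last dose and whether new therapy had started.
3. State in the SAP which causality categories make an event treatment-related, and for fatal events show 'not determined' separately from 'definitely' and 'possibly' related.
4. Reconcile the death rules in Protocol 7.1.3 with Table 7 and Section 7.2.2, so that sites handle a late death of unknown cause in the same way, and align the category labels in 7.1.3 and 7.3.1.

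The cost is a few sentences and one more output to program. The one real downside is that late related SAEs move from the main table to an adjacent one. No data are lost.

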- 10. Study treatment: The study treatment is CS1001 1200 mg, IV, Q3W, administered on the first day of each cycle after completing all the clinical and laboratory procedures/assessments.
- 11. Pregnancy test: Blood human chorionic gonadotrophin test is performed as a pregnancy test only in women of childbearing potential at screening (within 7 days before the first dose), EOT visit, and safety follow-up visit. An additional urine pregnancy test may be performed if clinically indicated. A serum pregnancy test is needed if the urine test reveals a positive result.
- 12. Hematology, serum chemistry, and urinalysis: Hematology includes complete blood count with differentials and hemoglobin. Serum chemistry tests include blood urea/urea nitrogen, creatinine, sodium, potassium, magnesium, chloride, calcium, phosphate, fasting blood glucose, total bilirubin, direct bilirubin, ALT, AST, alkaline phosphatase, lactate dehydrogenase, total cholesterol, total protein, and albumin. Urinalysis includes specific gravity, pH, urine glucose, urine protein, urine casts, ketones, and blood cells. These tests will be performed at screening (within 7 days before the first dose of investigational product), 3 days before each dosing starting from Cycle 2, EOT visit, and safety follow-up visit.
- 13. Coagulation function: Coagulation function tests including PT, APTT, and INR will be performed at screening.

- 14. Virology: Tests for HBsAg, HCV antibody, and HIV antibody will be performed at screening. Subjects who are HBsAg positive must receive further HBV DNA test. Subjects who are HCV antibody positive must receive further HCV RNA test.
- 15. Thyroid function: Thyroid function test including free triiodothyronine (FT3), free thyroxine (FT4), and thyroid stimulating hormone (TSH) tests will be performed at screening (within 7 days before the first dose of investigational product), thereafter 3 days before investigational product administration every other cycle (Cycle 3, 5, 7 and so on), EOT visit and safety follow-up visit.
- 16. EBV DNA: EBV DNA test will be performed at screening and 3 days before each dosing starting from Cycle 2. For subjects who achieve radiological CR, the EBV DNA test will be performed every other cycle thereafter.

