6.1.2 Treatment Period

Subjects will receive CS1001 1200 mg IV infusion every 21 days (3 weeks \pm 3 days). All visits will be conducted at the planned time points specified in the protocol.

The items to be completed during the treatment phase are listed in Table 4:

Table 4 Visit	procedures in	n the treatment	phase
----------------------	---------------	-----------------	-------

Items	Note		
Study Management Procedures			
Prior medications and concomitant medications	Concomitant medications are documented		
(Clinical Procedures and Assessments		
Adverse events	Adverse events are recorded		
Height, weight, and vital signs	Vital signs only; within 3 days before dosing in each cycle starting from Cycle 2		
Physical examination and ECOG performance status	Lymphoma-specific physical examination and ECOG performance status evaluation within 3 days before dosing in each cycle starting from Cycle 2		
Labo	oratory Procedures/Assessments (at site)		
Hematology, serum chemistry, urinalysis	Within 3 days before dosing in each cycle starting from Cycle 2		
Thyroid function tests	Within 3 days before dosing every other cycle starting from Cycle 3 (Cycles 3, 5, 7, and so on)		
EBV DNA	Blood sample for EBV DNA test will be collected at each cycle starting from Cycle 2 and every other cycle after radiological CR		
Laboratory 2	Procedures/Assessments (by central laboratory)		
РК	• Blood samples will be collected within 60 minutes before dosing as pre-treatment samples at Cycles 1, 2, 3, 4, and 8, and within 30 minutes after completion of infusion at Cycles 1 and 4		
ADA	• Pre-treatment blood samples are collected (within 60 minutes before dosing) at Cycle 1, 2, 3, 4 and every 4 cycles thereafter (e.g., Cycle 8, 12, 16, and so on)		
Efficacy Evaluation			
Radiology	 Contrast-enhanced CT will be performed every 12 weeks after the first dose of investigational product. Examined sites include head 47/104 		

Confidential

Items	Note
	and neck region (that must include nasal cavity, palatum durum, anterior cranial fossa, and nasopharynx), chest, abdomen, and pelvis. For patients allergic to CT contrast media, enhanced MRI will be used as an alternative.

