7.6 LIVER FUNCTION TEST FINDINGS

If ALT or AST > 3 x ULN with elevation in total bilirubin (>2 x ULN), it will be considered as a marker of severe liver injury after ruling out Cholelithiasis or other clinical jaundices that may lead to bilirubin. Therefore, any of the following events must be reported as an AE by the investigator:

- During the course of treatment, ALT or AST > 3 x baseline level; or ALT or AST >2 x baseline level and total bilirubin > 2 x ULN (direct bilirubin 35%) in a subject with baseline transaminase elevation;
- ALT or AST > 3 x baseline level with clinical jaundice during the course of treatment.

The most appropriate diagnosis or clinical test finding (if diagnosis unestablished) will be recorded in the eCRF and reported to the sponsor within 24 hours when the investigator gets aware of it, whether it's an SAE or not.

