Grading of laboratory data

Laboratory data will be derived programmatically according to the NCI CTCAE version 4.03. The calculation of CTC grades will be based on the observed laboratory values only, clinical assessments will not be considered. A shift table will be produced to reflect the grade change at the worst post-baseline assessment from the baseline visit.

Liver function parameters

The number and percentage of subjects with Liver Function Laboratory Findings will be summarized based on the event criteria as below:

Parameter	Criteria
ALT	>3xULN; >=5xULN; >=10xULN; >=20xULN
AST	>3xULN; >=5xULN; >=10xULN; >=20xULN
ALT or AST	>3xULN; >=5xULN; >=10xULN; >=20xULN
Total bilirubin (TBIL)	>=1.5xULN; >=2xULN
ALP	>=1.5xULN
ALT and/or AST & TBIL	ALT and/or AST>3xULN & TBIL >=1.5xULN ALT and/or AST>3xULN & TBIL >=2xULN
ALT and/or AST & TBIL & ALP	ALT and/or AST>3xULN & TBIL >=2xULN & ALP <2xULN

For a combined criterion to be fulfilled, all conditions have to be fulfilled on the same visit. The criteria are not mutually exclusive, e.g., a subject with ALT = 6.42xULN is counted for ALT >3xULN and ALT>5xULN.

12-Lead Electrocardiogram (ECG)

The analyses of 12-lead ECG data are based on the safety analysis set.

Overall interpretation of 12-lead ECG results will be summarized by visit.

Patient listing of clinically significant abnormal 12-lead ECG results will be provided.

ECOG Performance Status

The analyses of ECOG performance status are based on the safety analysis set.

Shift table will be produced for ECOG performance status at highest post-baseline visits and baseline.

Vital Signs

The analyses of vital signs are based on the safety analysis set.

Each vital sign parameter at each visit will be summarized, along with the absolute change from baseline.

MISSING DATA

The imputation for missing results will not be performed. The censoring rules for efficacy endpoints can be found in section 4.5.

Missing/Incomplete dates will be imputed according to Appendix 3. The output of listings will display the dates before imputation.

INTERIM ANALYSES

No formal efficacy interim analyses are planned.

LIST OF ABBREVIATION

Abbreviation	Full Name of Abbreviation
ADA	Anti-drug Antibody
ADAAS	Anti-drug Antibody Analysis Set
CI	Confidence Interval
CR	Complete Response
CT	Computed Tomography
CTCAE	Common Terminology Criteria for Adverse Events
CV	Coefficient of Variation
DoR	Duration of Response
EAS	Efficacy Analysis Set
ECOG	Eastern Cooperative Oncology Group

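### The same-visit rule in SAP 4.7.4 leaves some sequential ALT/AST-then-bilirubin rises out of the combined liver rows; windowed rows and a listing would be a cheap addition (minor)

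*SAP*

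**What the plan says.** SAP section 4.7.4, under liver function parameters, tabulates single-parameter limits for ALT, AST, bilirubin and ALP, followed by three combined rows. Two pair a transaminase with bilirubin: "ALT and/or AST>3xULN & TBIL >=1.5xULN ALT and/or AST>3xULN & TBIL >=2xULN". The third adds ALP: "ALT and/or AST>3xULN & TBIL >=2xULN & ALP <2xULN". The concurrency rule for all three is "For a combined criterion to be fulfilled, all conditions have to be fulfilled on the same visit". The section gives no time window, no version based on values at any time, and no subject listing for these rows.

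Protocol section 7.6 describes the same kind of signal: "If ALT or AST > 3 x ULN with elevation in total bilirubin (>2 x ULN", of which it says "it will be considered as a marker of severe liver injury" once certain other causes are excluded. It does not say whether the two values must come from one sample.

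Footnote 12 of the protocol's schedule of activities places chemistry at screening and then "3 days before each dosing starting from Cycle 2, EOT visit, and safety follow-up visit". Protocol section 6.1.2 sets the cycle: "Subjects will receive CS1001 1200 mg IV infusion every 21 days", with a window of 3 days either way.

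**The concern.** In a sequential pattern the transaminase rises first and bilirubin follows. If ALT/AST has dropped to 3xULN or below by the visit at which bilirubin is raised, no single visit meets both limits. The same happens if both are above their limits only between two visits. Either way the subject is missing from the combined rows, although both values may be in the database.

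Hepatitis is among the immune-related events that the protocol expects (section 1.2.3 and Appendix 13.4), so readers of the study report will look at these rows. The trial plans about 80 subjects, and one subject is 1/80 = 1.25% of the safety set. Suppose the true rate of such a finding were 0.5% to 1% (an assumption). The chance of seeing any case in 80 would then be 1 − 0.995^80 = 33% to 1 − 0.99^80 = 55%. One uncounted subject could change the row from one to zero.

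**Working it through.** The plan states no figure to reproduce. What follows illustrates the counting rule and does not estimate how often cases are lost.

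**Inputs from the documents.** Chemistry every 21 days; ALT/AST limit 3xULN; bilirubin limit 1.5x or 2xULN; all limits at one visit.

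**Assumptions.** ALT/AST is above its limit from day 0 to day A. Bilirubin is above its limit from day L (the lag) to day L + B, with B = 14. Labs fall on an exact 21-day grid with uniformly random phase, and there are no unscheduled tests. The comparison rule accepts a raised bilirubin on the same day as, or up to 30 days after, a lab with raised ALT/AST.

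**Same-visit rule.** A lab must fall in the overlap:

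P(same) = min(1, max(0, min(A, L + B) − L) / 21).

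**Window rule.** It also counts phases in which a lab on day a has raised ALT/AST and the next lab, on day a + 21, has raised bilirubin. For L ≤ 21 this needs a between 0 and min(A, L + B − 21). Phases already counted by the same-visit rule are not counted twice.

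| A (days) | L (days) | Overlap (days) | Same-visit | Days added by window | Window |
|---|---|---|---|---|---|
| 14 | 7 | 7 | 7/21 = 33% | 0 | 7/21 = 33% |
| 14 | 10 | 4 | 4/21 = 19% | 3 | 7/21 = 33% |
| 14 | 14 | 0 | 0% | 7 | 7/21 = 33% |
| 21 | 14 | 7 | 7/21 = 33% | 7 | 14/21 = 67% |
| 28 | 14 | 14 | 14/21 = 67% | 0 (already counted) | 14/21 = 67% |

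The loss runs from none to all of the cases that the window would find. It is zero when ALT/AST stays raised throughout the bilirubin rise (last row). It is also zero when bilirubin has recovered before the next lab (first row).

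**Sensitivity to B.** Longer bilirubin elevations widen the range:
- A = 14, L = 7, B = 21: 7/21 = 33% against 14/21 = 67%. The agreement at a 7-day lag in the first row therefore depends on B = 14.
- A = 28, L = 21, B = 28: 7/21 = 33% against 100%.
- A = 28, L = 7, B = 28: the overlap is 21 days, so both rules capture 100%.

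**Sensitivity to the window.** On an exact grid, labs are 21 or 42 days apart. Any window from 21 to 41 days gives the results above, and a window shorter than 21 days adds nothing. In practice the gap between consecutive pre-dose labs can be longer. Two doses at opposite ends of their 3-day windows are up to 21 + 3 + 3 = 27 days apart, and sampling the first up to 3 days early makes 30. If the window instead applies to the interval since the previous dose, the figure is 24 + 3 = 27. A delayed dose can lengthen the gap further, and Grade 2 hepatitis is on the withholding list in protocol section 5.3.2.

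**The case against.** The strongest reply is that the rule asks for all limits at one visit, not for both peaks. A reader might infer that any bilirubin rise following the transaminase is lost. That is wrong: it is counted whenever ALT/AST is still above 3xULN at that visit, and two rows of the illustration show no loss. The documents give no time course that would say which pattern is likely. This stands and sets the scope of the point.

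A reader might also infer that the SAP contradicts protocol section 7.6. It does not. Section 7.6 is silent on timing, and its wording can be read as concurrent.

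Next, the 21-day grid understates actual sampling. Section 6.2.4 recommends a retest in 24 hours for unexplained or unexpected findings judged clinically significant. Section 7.4 asks, where possible, for a revisit within 3 days for clinically significant Grade 3 or 4 findings. A decision to stop treatment leads within 7 days to an end-of-treatment visit with chemistry. Denser sampling makes it likelier that an existing overlap is caught. It cannot help when there is no overlap, and the SAP does not say how results from the unplanned-visit page (section 6.1.4) enter these rows.

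Finally, this table is not how liver injury is detected during the trial. Section 7.6 has its own reporting triggers, with notice to the sponsor within 24 hours whether or not the event is serious. The SAP keeps the single-parameter rows, the worst-grade shift table and a listing of all adverse events. This also stands, and it is why the point is minor. But none of these summaries shows that both rises occurred in sequence in one subject, and the triggers in section 7.6 use multiples of baseline for the transaminases, not the SAP's limits.

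**Conclusion.** The point holds in a limited form. The same-visit rule leaves out of the three combined rows those subjects whose ALT/AST has fallen to 3xULN or below by the visit with raised bilirubin, and those whose overlap no lab samples. With bilirubin raised for 14 days, the illustration gives capture of 0% to 67% for the same-visit rule and 33% to 67% for a 30-day window. The difference appears when ALT/AST falls before or during the bilirubin rise. These figures rest on assumed durations, lags and window, and on no unscheduled testing.

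A reader might go further and infer that serious liver injury could go unnoticed in this trial. The documents do not support that: the values stay in the database, the single-parameter counts and shift tables remain, and adverse event reporting does not depend on this table. The primary endpoint is untouched. Severity: minor.

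**What to change.** In SAP section 4.7.4:

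- Keep the three same-visit rows.
- Add matching rows that count bilirubin >=1.5xULN and >=2xULN on the same day as, or within a prespecified window after, ALT and/or AST >3xULN. Do the same for the row with ALP, and state at which sample the ALP limit applies.
- State the window length and justify it. Thirty days is only an example; the choice is the sponsor's and should allow for the longest expected gap between labs.
- State that scheduled and unscheduled results both count.
- List every subject who meets either version, with dates and values.

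The cost is a few table rows and one listing from data already collected, with no change to trial conduct. The downside is that some added cases will have other causes and need medical review. For example, subjects with Gilbert's disease may enter with bilirubin up to 3xULN.
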